Very little formal investigation has been performed to study the influence of age on hip arthroscopy outcomes; as such, there is currently no consensus on age as a predictor of outcome. Khanduja and Villar¹² recommend arthroscopy to be reserved for patients aged less than 50 years old. Philippon et al.³² reported outcomes after FAI in patients aged 50 years or older at a minimum 1-year follow-up and found that patients primarily achieved surgical success, though with a 20% conversion to total hip replacement (with a higher incidence in patients with > 2 mm of joint space). Larson et al.²⁴ also showed a failure rate that was dependent on age; however, a formal comparison was not made. Byrd and Jones³⁹ showed worse outcomes in older men. Although there have been studies looking at age secondarily in patients with labral tears, there is no prospective evidence to endorse or refute a recommendation of hip arthroscopy for patients of any age being treated for a tear of the acetabular labrum.

Preliminary Data

Our group recently performed a large retrospective case-control series looking at the influence of pre-operative arthritis and age as predictors of long-term outcomes following arthroscopic labral repair.⁴⁰ Over the course of the study period, which spanned 8 years and 200 patients, our management evolved to reflect the current practice of abstaining from arthroscopy in patients with less than 2 mm of joint space on plain standing radiographs. In spite of this, we continue to routinely encounter cartilage defects intra-operatively. Such findings can be explained by evidence stating conventional radiographic measures are poor predictors of actual arthritis in the hip.⁴⁸ Although it is possible that focal cartilage defects seen at arthroscopy are incidental findings.⁴²

Most studies attempt to eliminate radiographically evident severe arthritis by excluding patients who demonstrate less than 2 mm of joint space on standing antero-posterior hip radiographs at the time of surgery. However, based on our results, we suggest that the presence of Outerbridge grade 4 arthritic changes noted at the time of arthroscopy can be used adjunctively to identify patients who will fare poorly after hip arthroscopy for labral pathology. Interestingly, despite the apparent influence of arthroscopically identified arthritis portending worse outcomes (Odds ratio=2.5), our preliminary results suggest age is a stronger predictor (Odds ratio = 7) of diminished surgical outcomes.

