Determining which patients, using age and arthritic burden as predictors, can benefit from labral repair is paramount for several reasons. Showing arthroscopic repair is of little or no benefit to a specific cohort can reduce the number of unnecessary surgeries performed, increase the use of conservative therapy (if validated) and reduce the interval between diagnosis and total hip replacement. Additionally, proving a benefit exists from arthroscopic repair in a certain subset of the population will substantiate the need for developing a treatment algorithm in older patients presenting with labral tears and some degree of pre-existing arthritis. Furthermore, conservative physical therapy may prove to be of equal or greater benefit than arthroscopic repair in select patients. If true, this study will be a landmark for providing the evidence needed to recommend conservative treatment as an efficacious alternative in addition to providing a foundation for future research on this topic.

II. SPECIFIC AIMS:

Specific Aim 1: To evaluate if physical therapy alone or arthroscopic labral repair and physical therapy is of greater benefit to patients presenting at age 40 with tears of the acetabular labrum.

Hypothesis 1.1: Physical therapy will result in a significant difference in mHHS scoring at 12 months when compared to baseline.

Hypothesis 1.2: Arthroscopic labral repair will result in a significant difference in mHHS scoring at 12 months when compared to baseline.

Hypothesis 1.3: Arthroscopic labral repair and physical therapy will be superior to physical therapy alone in improving function and alleviating symptoms at 12 months when compared to baseline, as judged by the mHHS.

Hypothesis 1.4: Hypotheses 1.1-1.3 will hold true at 24 months and beyond.

Hypothesis 1.5: Functional outcome scores collected at the completion of PT will not significantly differ from those collected at 12 and 24 months and beyond in the same group.

Specific Aim 2: To evaluate the effect of arthritic burden on short term outcomes following arthroscopic labral repair.

Hypothesis 2.1: In the surgical treatment group, subjects with arthroscopically proven severe osteoarthritis (Outerbridge grade 4) will do more poorly on validated outcome measures, specifically the mHHS, after arthroscopy than subjects with less severe osteoarthritis (Outerbridge grade ≤ 3).

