Hypothesis 2.2: Cartilage defects at or near the chondrolabral junction are prognostic indicators of worse outcomes as determined by the mHHS.

Hypothesis 2.3: Subjects with any degree of joint space narrowing (classified by Tonnis and Kellgren-Lawrence grading, see below) on plain radiographs will have more pain, regain less function, and do more poorly based on validated outcome measures, specifically the mHHS, at 6 and 12 months than subjects without any degree of joint space narrowing on plain radiographs.

EXPLORATORY Specific Aim 3: To evaluate the relationship between joint space narrowing on plain radiography and arthroscopically proven osteoarthritis.

Hypothesis 3.1: Tonnis grading and Kellgren-Lawrence grading on plain radiography are not predictive of the severity of arthritis at the time of arthroscopy.

Specific Aim 4: To analyze the data of subjects crossing over from PT alone to PT and surgery.

Hypothesis 4.1: Primary outcome scoring (mHHS) at 12 and 24 months after cross to surgery and PT will differ significantly from those initially randomized to surgical treatment.

Hypothesis 4.2: Baseline scores on outcome measures of those subjects crossing over will not differ significantly from those obtained at the time of crossover.

III. SUBJECT SELECTION & ENROLLMENT:

Study Overview: This is a prospective randomized control trial (RCT), which will enroll subjects with a clinically diagnosed tear of the acetabular labrum. Subjects who have been diagnosed with a labral tear in clinic will receive conservative physical therapy treatment alone or arthroscopic surgical labral repair and physical therapy. If it is discovered that there is unexpected pathology at the time of arthroscopy for subjects in the surgery group, those subjects will be removed from the study. This is due to the possibility that the source of pain is less likely a result of the dysfunction of the labrum and more likely due to aberrant extra-articular biology. We will use validated outcomes measures that include the mHHS, LEFS, HOS, NAHS, and iHOT-33 (see below) and review the medical record for physical exam findings to track patient progress throughout their involvement in the study which will continue for as long as they are a patient of the PI. Study procedures will be complete when the last enrolled subject completes 24-month follow-up and completes the corresponding surveys.

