Using the data from our retrospective review of outcomes following labral repair, a 10 point or greater difference on the mHHS as significant, and a single-tail independent t-test to evaluate the difference between means with 80% power and a 5% significance level, 35 subjects are needed to demonstrate a statistically significant difference between the average mHHS of the conservative group and surgical group. Testing of hypothesis 1.5 will be an intragroup analysis looking for a significant difference in outcome measures from the time of completion of PT (non-crossover) when compared to the same data to be collected at 12 months and 24 months. The purpose is to determine the short-term durability of the response to PT, if one is found.

70 study completers should provide us with the necessary data needed to substantiate or reject our hypothesis. There has been no prospective trial to date testing these hypotheses in the hip, but we expected a 7.3-10.3% dropout rate based on the results of a similar study in the knee. However, as of July 2018, we had 47 patients that had passed the 2-year follow-up mark, of which 5 patients were no longer in the study (combination of lost to follow-up and proceeding to total hip arthroplasty), and another 11 had yet to complete their 2-year surveys even with multiple attempts to contact them and encourage them to do so. With a yield of 31 patients out of 47, or 65.95%, we increased our sample size to 122.

Therefore, we estimate needing 122 subjects to achieve 70 study completers, in the appropriate proportion of 35 subjects per treatment arm. We enroll until reaching at least 35 subjects in each group.

The results of the MeTeOR trial in the knee show that we can expect a higher drop-out rate in the surgical group. As such, this cohort may be our limiting factor.^{40, 43, 61, 62}

Specific Aim 2. Hypotheses 2.1-2.3: *To evaluate the significance of arthritic burden on short term outcomes following arthroscopic labral repair.*

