Hypothesis 2.1 was powered on the basis of our prior work where 33% of study participants had grade 4 Outerbridge changes the time of arthroscopy. Dividing our cohort into two subgroups: 1) Those with grade 4 changes and 2) Those without. We will need 12 subjects with grade 4 changes in order to perform adequate sub-group analysis.⁶³ Powered to 80% and 5% significance level. Hypothesis 2.2 is another sub-group analysis that will be conducted in a similar fashion to that of hypothesis 2.1. However, the two groups will be categorized into: 1) cartilage defects at or near the chondro-labral junction and 2) cartilage defects not at or near the chondro-labral junction. We cannot control the heterogeneity of the subjects enrolled, but based on this analysis we expect to meet our target enrollment. Hypothesis 2.3 will be analyzed via linear regression and is appropriately powered.

Specific Aim 3 is exploratory. Since we are recruiting subjects for the main purposes of determining outcomes, we recognize that we may be underpowered for the definitive analyses of our radiographic correlation hypotheses. Nevertheless, we anticipate that we will enroll sufficient numbers of subjects to draw an association or at the very least, trend patient outcomes with degree of joint space narrowing, Kellgren-Lawrence grading, and Tonnis grading. There should also be sufficient numbers to preliminarily assess any correlations between pre-operative Kellgren-Lawrence and Tonnis grades with the Outerbridge classification at the time of arthroscopy.

VI. RISKS & DISCOMFORTS

Conservative Treatment: Subjects can expect the routine discomfort associated with any therapeutic procedure. Complications may include muscle soreness, pain, and increased edema or muscle fatigue.

Operative treatment: Since surgery is not considered a research procedure (only the randomization into the surgery group is considered a research procedure, as explained above) surgical risks are explained in the surgical consent process.

In the rehabilitation period, patients will be subject to the same potentials discomforts as those subjects in the conservative treatment group as the physical therapy protocols for both groups are identical. In both treatment groups every effort will be made to minimize the risk of adverse events and patient discomfort.

VII. POTENTIAL BENEFITS:

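### Hypothesis 2.3 is called appropriately powered with no inputs given; with Aim 1's figures borrowed, power for 10 points is below 80% on most readings

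*Combined protocol and SAP*

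**What the plan says.** Hypothesis 2.3 (Section II, Specific Aim 2) contrasts "Subjects with any degree of joint space narrowing", graded by Tonnis and Kellgren-Lawrence, with the rest. It predicts worse results on the mHHS "at 6 and 12 months than subjects without any degree of joint space narrowing on plain radiographs". The aim it belongs to is "To evaluate the effect of arthritic burden on short term outcomes following arthroscopic labral repair".

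Section V, Power Analysis, Specific Aim 2, disposes of its power in one sentence: "Hypothesis 2.3 will be analyzed via linear regression and is appropriately powered". By contrast, Hypothesis 2.1 in the same paragraph has a prevalence (33% with Outerbridge grade 4), a count (12 subjects) and the statement "Powered to 80% and 5% significance level".

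The next paragraph, on exploratory Aim 3, accepts that the radiographic analyses may not be powered for definitive conclusions. It expects enough subjects to show an association, or failing that a trend, between outcomes and the degree of narrowing and the two radiographic grades.

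The only full set of mHHS design figures is for Aim 1. It takes "a 10 point or greater difference on the mHHS as significant" and uses a one-tailed independent t-test, 5% significance, 80% power and 35 completers per arm. The SD is not reported.

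**The concern.** A reader cannot check the claim, because nothing is attached to it. The plan also points both ways. Outcome against joint space narrowing by these two gradings is in substance Hypothesis 2.3, yet one paragraph calls it appropriately powered and the next treats outcome against narrowing as something that may only be trended.

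Section I (Implications) wants age and arthritic burden to help decide who benefits from repair. If the narrowing test comes out null, a protocol statement of adequate power invites the conclusion that narrowing does not matter. A small or unevenly split sample may not support that conclusion.

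**Working it through.** No power figure is stated for Hypothesis 2.3, so there is none to reproduce. The check asks what power would result if Aim 1's design figures were carried over.

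**Inputs**
- Difference: 10 mHHS points (stated for Aim 1, borrowed here).
- Alpha: 5%, one-sided in Aim 1. Sidedness is not stated for 2.3, so both are shown.
- Number analysed: 35 surgical completers if Aim 2's title governs, or 70 completers if both arms are used.
- Prevalence of narrowing: not given; assumed 20%, 30% and 50%.
- SD: not given; back-solved below.

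**Formula.** Regression on a yes/no exposure, without covariates, is a two-sample t-test with an unequal split. With SE = SD × √(1/n₁ + 1/n₂), λ = 10/SE and df = n₁ + n₂ − 2, one-sided power is P(T > t₀.₉₅,df), where T is noncentral t with parameter λ. Two-sided power uses t₀.₉₇₅,df.

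**Step 1, the SD.** Setting one-sided power at 80% for 35 v 35 and 10 points gives SD = 16.66. The normal approximation agrees: 10 / [(1.645 + 0.842) × √(2/35)] = 16.8.

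**Step 2, one case in full.** For 18 v 17: SE = 16.66 × √(1/18 + 1/17) = 5.63 and λ = 10/5.63 = 1.78. The one-sided critical value on 33 df is 1.692, and power is 54%.

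**Step 3, all cases**

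| N | Narrowed v not | λ | One-sided power | Two-sided power | Detectable at 80%, two-sided (points) |
|---|---|---|---|---|---|
| 35 | 7 v 28 | 1.42 | 40% | 28% | 20.3 |
| 35 | 10 v 25 | 1.60 | 47% | 34% | 18.0 |
| 35 | 18 v 17 | 1.78 | 54% | 41% | 16.3 |
| 70 | 14 v 56 | 2.01 | 63% | 51% | 14.1 |
| 70 | 21 v 49 | 2.30 | 74% | 62% | 12.3 |
| 70 | 35 v 35 | 2.51 | 80% | 70% | 11.3 |

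The 80% in the last row holds by construction, since the SD was solved from it.

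**Step 4, larger numbers**
- All randomised surgical subjects, taking equal allocation: 122/2 = 61. An even split (30 v 31) gives 75% one-sided and 63% two-sided.
- Both arms at the plan's yield: 122 × 0.6595 ≈ 80. With a third narrowed, 80% one-sided and 70% two-sided. With an even split, 84% and 75%.
- Both arms with nobody lost (122, an upper bound), a third narrowed: 93% and 87%.

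**Step 5, wider prevalence.** At 10% narrowed, two-sided power is 18% for N = 35 and 32% for N = 70. The 20-50% range is therefore illustrative, not a bound.

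**The case against.** The strongest reply is that these are not the plan's figures for this hypothesis. The SD is back-solved, the 10 points come from a comparison of treatments, and the prevalence is assumed. That stands. A reader might infer that the plan's own numbers prove the test underpowered. They do not: a true difference of 15 points with a third narrowed would give 94% two-sided power at N = 70 (68% at N = 35).

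Several other points also stand.
- Hypothesis 2.3, unlike 2.1, does not name the surgical group, so a both-arms analysis is open. The surgical-arm reading comes from the title of Aim 2.
- N may exceed 35 or 70. The 65.95% yield is for two-year surveys, whereas 2.3 is tested at 6 and 12 months. Crossovers to surgery would add repaired hips.
- "Powered to 80% and 5% significance level" belongs to 2.1, and "70 study completers should provide us with the necessary data needed to substantiate or reject our hypothesis" belongs to Aim 1. Neither is a numerical claim about 2.3.
- One might infer an uneven split from the group's practice of "abstaining from arthroscopy in patients with less than 2 mm of joint space". That concerns hips below 2 mm, while 2.3 counts any narrowing, and the eligibility table has no joint-space exclusion. The split is simply unknown.
- Baseline adjustment would help. If baseline and follow-up mHHS correlated at 0.5 (an assumption), the SD would fall to 16.66 × √(1 − 0.25) = 14.4. Power would be about 84% one-sided and 75% two-sided at 21 v 49, but still at most 64% one-sided with 35 subjects.

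The Aim 3 caveat lessens the risk of misreading. It also confirms that the unqualified claim for 2.3 does not fit its surroundings. None of these replies supplies the missing inputs.

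**Conclusion.** The statement of adequate power for Hypothesis 2.3 is unsupported, and the following paragraph undercuts it. No stated number fails to reproduce, because none is stated.

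The size is conditional on a 10-point difference, an SD of about 16.7 and an unadjusted comparison. On the surgical-arm reading of Aim 2, 80% power is not reached at any split, even with all 61 randomised surgical subjects (75% one-sided at best). With both arms and 70 to 80 subjects, it is reached only one-sided, and only with a near-even split at 70 or with about a third or more narrowed at 80. Two-sided, it would need more subjects than the plan's yield implies, a larger true difference or useful covariate adjustment. It should not be said that power is a particular low figure, or that the test is shown to fail. The primary comparison is unaffected.

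**What to change.** In Section V, Power Analysis, Specific Aim 2:
- Delete the claim that 2.3 is appropriately powered.
- State the analysis population, N, assumed prevalence of narrowing, alpha, sidedness and the difference detectable at 80%, marked as conditional on those assumptions.
- Label 2.3 exploratory and report the estimate with its CI, so that a null result is read from the interval.
- Include baseline mHHS in the regression.
- If both arms are pooled, add treatment arm as a covariate and quote the power for that model, not the surgical-arm figure. State that the result is then no longer specific to outcomes after repair. Pooling is feasible, since hip radiographs are an inclusion criterion and the mHHS is collected in both arms.

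The cost is a few lines of text and no new subjects. The downside is a less favourable power statement.

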Our Primary Outcome is change in the modified Harris Hip Score at 12 months and 24 months. Secondary outcomes include changes in other validated outcomes measures patient satisfaction, and degree of improvement on physical exam. The influence of OA severity (Outerbridge scoring) and location of OA will also be analyzed to determine if they have an effect on the aforementioned outcome measures. Satisfaction will be assessed by an exit questionnaire (See section IV). In addition to gauging satisfaction, this questionnaire will ask subjects how they felt about their participation in the study. (See section IV)

Inclusion and Exclusion Criteria:

Inclusion criteria	Rationale
Age 40 or greater	Higher likelihood of undetectable OA on imaging
Orthopedic surgeon determines symptoms are consistent with a labral tear.	Required for treatment
Availability of hip radiographs and MRI	Needed to assess eligibility and comparison for specific aim 3
Willingness to undergo randomization and ability to understand and sign informed consent document	Ability to understand study and consent willingly

Exclusion criteria	Rationale
Unexpected pathology at the time of arthroscopy	Source of pain less likely to due dysfunction of the labrum and more likely due to aberrant extra-articular biology
Same site surgery	Complex anatomy
Contraindication to surgery or physical therapy	Cannot tolerate either treatment grouping
Alternate form of PT for greater than 6 weeks	Will negatively augment results. May affect recruitment.

Selection and enrollment:

We will enroll 122 consecutive subjects meeting the aforementioned criteria. Subjects will be randomized into conservative or surgical treatment arms. All potential subjects on the clinic schedule of the investigator will be pre-screened for eligibility based on age, clinical assessment, and previous medical history.

All eligible subjects will be approached at an outpatient clinic visit. Those who initially meet inclusion criteria will be introduced to the study and given a research consent form that they have the opportunity to take home and to review.

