The mean outcome scores of the mHHS in each treatment group at 12 months will be compared to baseline scores to assess for significant differences using paired sample t-test in SPSS 16 (SPSS, Chicago, IL). The mean outcomes scores of the mHHS between groups at 12 months will be compared using independent t-tests to assess for significant difference. We will use a Levene test to judge variance and proceed accordingly. If a statistically significant difference is detected during these analyses, we will calculate the effect size (ES) to determine how meaningful these results are outside of being statistically significant. The ES will be calculated by: [(mean mHHS score of surgical arm / mean mHHS of the conservative group) / standard deviation of the conservative group]. According to Cohen ⁵⁸, an ES <0.1 is trivial, ES of 0.1-0.3 is minimal, ES of 0.3-0.5, is moderate, and ES >0.5 is large. We will repeat the same analysis at 12 months.

Hypothesis 2.1, 2.2, and 2.3:

Diagnosis and treatment of the prearthritic and early arthritic hip has been an area of intense interest. However, our most conventional method of assessment (plain radiography) does not provide us with enough diagnostic sensitivity.⁴¹ Direct visualization on the articular surfaces in the hip is both sensitive and specific. Furthermore, emphasis is being placed on the location of arthritis as a prognostic indicator of good outcomes following hip arthroscopy. The value of arthroscopic techniques for primary

symptoms and/or prevention of OA secondary to labral tears remains unclear even though preliminary reports indicate there may be some benefit to repairing a torn labrum, even in cases of severe OA. Evaluation of arthritic change at the time of arthroscopy is important, particularly in subjects where there remains uncertainty about the efficacy of labral repair for those with articular or rim cartilage degeneration that the effects of those changes on long-term OA progression.⁵⁹

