1. The study staff will meet regularly with [name] to review study participants and the data that has been collected on them to date. If a subject becomes disqualified or must leave the study for safety concerns, [name] will personally inform them of the situation through the subjects preferred method of contact. [name] will be leading and administering the conservative arm of the study (subjects being treated non-surgically with physical therapy and subjects in the post-operative period receiving rehabilitative physical therapy). She will inform [name] of patient progress and any potential clinically significant events that may warrant further discussion and could ultimately result in the dismissal of a patient from the study.
 - a. As this is a prospective study comparing the gold standard of treatment (labral repair) to a potentially equivalent therapeutic modality, qualifying subjects will never be denied the option to undergo labral repair via hip arthroscopy. The treatment schema allows for subjects in the non-surgical arm (physical therapy alone) to cross over to the surgical treatment group at any time (following physical therapy) from initial enrollment if they wish to do so. Subjects who decide to crossover or are indicated to crossover through the non achievement of advancement criteria will have the PT discontinued at that time point but must wait for official crossover at 6 weeks after initial enrollment. Participants can always decide to leave the study if this is not what they want. The decision to cross over will in no way affect the quality of healthcare current or prior study participants receive. All of this will also be explained to them during the consent.
 - b. We will review all data continuously and should there be a obvious clinical detriment to specific treatment arm such as repeated poor outcomes or worsening function, further investigation will be initiated to determine if this is an isolated occurrence or if there is a significant trend which warrants cessation of study protocol and disenrollment of subjects.
 - i. Stopping rules include a clear difference in morbidity, as measured by interval physical exams and outcomes questionnaires, between treatment groups
 - ii. Any significant mortality possibly linked to study procedures will result in immediate suspension of the study protocol.

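### Subjects who have a hip replacement or are dismissed can fall out of the primary mHHS comparison, because no rule keeps them in follow-up or in the analysis

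*Combined protocol and SAP*

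**What the plan says.** Section VIII (Monitoring and Quality Assurance), item 1, describes two ways in which a subject may leave. The physical therapy lead reports progress and clinically significant events to the investigator, and these "could ultimately result in the dismissal of a patient from the study". The same item sets out how a subject is told "If a subject becomes disqualified or must leave the study for safety concerns". It gives no criteria for either route and does not say whether surveys continue or how the subject's data are treated.

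Section V, Power Analysis, reports the position in July 2018. Among 47 subjects past the 2-year mark, "5 patients were no longer in the study (combination of lost to follow-up and proceeding to total hip arthroplasty"). A further 11 had not returned 2-year surveys despite repeated contact. Both groups are left out of the yield of 31. The trial is sized on the statement that "70 study completers should provide us with the necessary data needed to substantiate or reject our hypothesis".

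On the endpoint, Section III states: "Our Primary Outcome is change in the modified Harris Hip Score at 12 months and 24 months". Hip replacement is not among the primary or secondary outcomes listed there. Section V gives the between-group analysis: "The mean outcomes scores of the mHHS between groups at 12 months will be compared using independent t-tests to assess for significant difference". Neither section states an as-randomised analysis set, a missing-data method, or a rule for mHHS after hip replacement.

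The removal of surgery-arm subjects with unexpected pathology at arthroscopy (Section III, Study Overview: "those subjects will be removed from the study") is a separate matter and is not counted here.

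**The concern.** Hip replacement is not incidental in this trial. The Background (Age) cites a series of patients aged 50 or older in which 20% converted to hip replacement, and the Implications paragraph gives a shorter interval from diagnosis to replacement as a reason for doing the study. A subject who needs a replacement has, on that rationale, done badly on the assigned treatment. If such subjects leave the study and only the remaining scores are averaged, the failure lowers no mean and is counted under no other outcome.

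Dismissal raises the same issue in weaker form. It follows a clinical event, has no written criteria, and has no provision for continued follow-up. Treatment is not blinded and Section VIII, item 2 dispenses with a data monitoring board, so nobody independent would see whether removals differ by arm.

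At stake is the comparison in Hypothesis 1.3 (surgery plus physical therapy against physical therapy alone), and its extension to 24 months in Hypothesis 1.4, where the 2-year losses bear most directly.

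**Working it through.** **Step 1: the plan's own figures.** The yield is (47 − 5 − 11)/47 = 31/47 = 65.96%; the plan prints 65.95%. The 5 who are out are 5/47 = 10.6%, and the 11 non-responders are 11/47 = 23.4%. At that yield, 70 completers need 70/(31/47) = 106.1, so 107 enrolled and not the stated 122. That mismatch is a separate matter. Enrolling 122 would give about 122 × 31/47 = 80 completers, which helps precision but does not remove bias from outcome-related loss.

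**Step 2: follow a hip-replacement subject through the text.**
- The Power Analysis places the subject among the 5 who are out, apart from the 11 still being contacted.
- The sample size counts only completers.
- The t-test in Section V compares means and names no population that would bring the subject back.
- The outcome list in Section III does not record the replacement.

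A dismissed subject is in the same position, except that the documents do not report any such case.

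**Step 3: what a loss of this kind does to one arm.** Let a fraction f of an arm be missing, and let those subjects average D points below the rest, whose mean is m. The full-arm mean is (1 − f)m + f(m − D) = m − fD. The retained mean is m, so it is too high by fD.

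The documents give no value for D, so it is assumed over a range. With f = 5/47 = 0.106:

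| D (points, assumed) | Shift fD (points) |
|---|---|
| 10 | 1.1 |
| 20 | 2.1 |
| 30 | 3.2 |
| 40 | 4.3 |

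The reference is the 10-point mHHS difference used in the Power Analysis.

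**Step 4: from one arm to the comparison.** The between-arm bias is f(surgery) × D(surgery) − f(PT) × D(PT). If the two products are equal, the bias is zero. If 10.6% is lost from one arm only, the bias is 1.1 to 4.3 points in favour of that arm, whichever arm it is.

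**Step 5: how far 10.6% can be trusted.**
- It mixes hip replacement with ordinary loss to follow-up and the split is not given, so it is an upper bound on the pooled share with hip replacement.
- It pools the arms. It does not bound a single arm: if the 47 were evenly split and all 5 came from one side, f would be 5/23.5 = 21.3% there. Nothing indicates that this happened.
- It is a 2-year count. A subject whose hip was replaced after month 12 may already have given a 12-month score.

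**The case against.** The strongest reply is that the plan is silent here and not wrong. Section IV says surveys continue, remotely if needed, until subjects ask to stop, and Section III says tracking lasts as long as the subject is the investigator's patient. The dismissal sentence reads as ordinary safety wording. The phrase about completers stands in the sample-size paragraph and does not define the analysis population.

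Much of this stands, and it rules out several stronger readings:
- A reader might infer that dismissal is a route for removing treatment failures. The text does not say so. Failure of physical therapy has its own path: unmet advancement criteria lead back to the surgeon and possibly to crossover, and crossovers stay in the study with their own scores under Aim 4.
- A reader might infer that dismissals have already happened. The July 2018 count names loss to follow-up and hip replacement only.
- A reader might infer that collected data are deleted, or that the analysis is restricted to completers. Neither is stated; the second is an inference from the sizing and from the absence of any analysis set.
- Section VIII, item 1b mentions disenrolment after poor outcomes, but in the context of halting the study protocol and not of removing individuals.

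The continuing-survey provision does not dispose of the point. The Power Analysis separates those who are out from those still being asked for surveys and puts hip-replacement subjects in the first group. The practice it describes is therefore that replacement ends participation, and nothing elsewhere reverses that.

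**Conclusion.** The point holds as a gap with a demonstrated consequence: hip replacement has been treated as leaving the study, dismissal carries no follow-up provision, and the planned t-test has no as-randomised population to hold either group in. Outcome-related losses can therefore drop out of the primary comparison and, for hip replacement, out of the reported outcomes altogether.

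Its size is not known. The 1.1 to 4.3 points rest on three assumptions: that 10.6% is lost from one arm, that those subjects would score 10 to 40 points lower, and that none of them contributes a score at the time point analysed. The range illustrates a shift in one arm's mean and does not estimate the trial's bias.

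A reader might also infer that the bias favours surgery, because the Power Analysis expects more dropout there. That expectation is borrowed from a knee trial, and the protocol does not say that those dropouts are failures. The direction stays open.

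The change should be made, with medium confidence: the text on hip replacement is clear, while its effect on the result cannot be sized.

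**What to change.** - State in Sections IV and VIII that hip replacement, or dismissal from study treatment, does not end follow-up unless the subject withdraws consent. Keep sending the 12- and 24-month surveys to these subjects through REDCap.
- State in Section V that all randomised subjects are analysed in their assigned arm, including scores collected before a replacement or dismissal.
- Report the number of hip replacements by arm, and the number of and reasons for dismissals.
- Prespecify one rule for mHHS after hip replacement, and at least one sensitivity analysis that treats replacement as a poor outcome. Examples are the last score before replacement, or a worst-rank analysis, which needs a rank-based test in place of the t-test. More than one main rule is defensible. Scores taken after a replacement may reflect the new joint, so the choice should be explained.

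The cost is protocol wording, some extra contact effort using surveys that already exist, and modest additional analysis. No treatment decision changes.
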